8 STATISTICAL PLAN

8.1 Statistical methods:

Analysis for each Aim: Specific Aim 1: To determine the effects of the Tai Chi intervention on functional performance over a one-year period in poor, multiethnic, elderly residents of subsidized housing facilities. The primary functional outcome will be the Short Physical Performance Battery (SPPB) score. We will also examine the effects of Tai Chi on self-reported physical and mental health, gait and balance, falls, executive function, social engagement, overall activity level, and other patient-centered outcomes.

The effect of the Tai Chi intervention on functional performance as measured by SPPB will be estimated from a shared-baseline linear mixed model with fixed effects for age, follow-up time, age x time interaction, and treatment x time interaction and random effects of community, site within community, participant within site, community x treatment, community x time, community x treatment x time, site x time, and participant x time interactions. The shared baseline across treatment groups reflects homogeneity of the population with respect to treatment prior to random assignment and adjusts for effects of baseline level in a manner equivalent to ANCOVA. The random effects acknowledge the expected correlations among sites within a community, among participants within a site, and among repeated longitudinal assessments of each participant. This approach also naturally accommodates unequal enrollment across sites and loss to follow-up, even potentially informative loss to follow-up, if well predicted by the observed data on participants prior to drop-out. All participants will be included in the primary analysis according to their treatment assignment, following the intention-to-treat principle. Primary inference will be based on a two-tailed test at alpha = 0.023 of the fixed treatment x time interaction estimating Tai Chi-dependent improvement in rates of change in SPPB. An additional alpha = 0.002 is reserved for one interim analysis. The total two-tailed alpha = 0.025 for testing SPPB preserves an overall type I error rate of 0.05 for the functional and utilization primary aims. In addition to intention-to-treat analyses, we will perform secondary per-protocol analyses, defining participants in a tai chi group as 'per-protocol' if they attended ≥50% of tai chi classes averaged over the year-long intervention.

Secondary continuous outcomes will be analyzed using the same model. Counts of falls will be analyzed in a similar mixed effect negative binomial regression. Both nominal p-values and step-down Bonferroni-adjusted p-values will be calculated for analyses of secondary outcomes. Secondary analyses will consider effects of treatment dose based on attendance records. Given the possible influence of perceived treatment efficacy on adherence, which could bias the effect of adherence on Tai Chi efficacy, these analyses will be exploratory. Other secondary analyses will determine if Tai Chi is more effective or uniquely effective for specific subgroups of participants by including fixed effects for subgroup indicators and their interactions with treatment, time, and treatment x time.

Interim analysis: One interim analysis for efficacy, futility, and sample size re-estimation is planned after all participants enrolled in wave 1 have completed their 12-month assessment (or dropped out). The study will be stopped for efficacy based on a two-sided Haybittle-Peto boundary at $\alpha = 0.002$ for each co-primary outcome. A non-binding proposal to stop the study for futility will be based on a beta spending rule linear in information time, or $\beta = 0.10$. The study will be stopped early for efficacy or futility only if both co-primary outcomes have demonstrated efficacy or futility. Observed drop-out and community-level, site-level, and participant-level variance components and their collective effect on the standard error of the treatment x time interaction term will be estimated. The benefit of increasing the number of sites or the number of participants per site will be considered based on the pre-specified minimum treatment effects of interest on SPPB and total health care utilization. Results of the efficacy and futility analysis will be shared only between an unblinded statistician and the DSMB. Estimates of the nuisance parameters and their effect on power for the pre-specified effect sizes will be shared with the study team given negligible risk of deducing the treatment effect and the importance of logistical constraints in planning any increase in sample size.

DURING THE CLOSED SESSION OF THE MOST RECENT DSMB MEETING ON OCTOBER 20, 2017, THE DSMB AND NIA PROJECT OFFICER REVIEWED THE STUDY REPORT, INCLUDING SAFETY DATA AND A PREPLANNED INTERIM ANALYSIS FOR THE PRIMARY

OUTCOME, SPPB - SHORT PHYSICAL PERFORMANCE BATTERY - USING 12 MONTH WAVE 1 DATA. RESULTS OF THE A PRIORI DEFINED INTERIM ANALYSIS INDICATED THAT THE PRESPECIFIED BOUNDARY FOR THE TRIAL CESSATION DUE TO FUTILITY WAS CROSSED. GIVEN THAT THE STOPPING RULE FOR FUTILITY WAS SATISFIED, THE DSMB RECOMMENDED DISCONTINUING THE MI-WISH TRIAL.

8.2 Sample size determination (include power calculations or provide justification for their absence, e.g., pilot/feasibility study):

Sample Size Calculation and Justification: Power for the primary analysis of SPPB (Short Physical Performance Battery) can be estimated by extrapolating results from our preliminary study in similar housing facilities where the mean baseline SPPB score was 8 out of a total possible score of 12. In a mixed model ANCOVA of 3-month change in SPPB that included a site-level random effect of treatment, the standard error for the fixed effect of treatment was 0.268. Extrapolating from 3 months to 12 and from 2 sites to 16 (each study with 20 participants per site), the estimated standard error for a treatment effect on 12-month change in SPPB would be $0.268 \times 12/3 \times \sqrt{2/16} = 0.379$. Given that estimate, the current study would have 85% power to detect a 1.38 point difference in 12-month change in SPPB based on a two-tailed test at $\alpha = 0.023$. Even with up to 20% loss to follow-up, the study will be well powered to detect treatment-dependent differences in 12-month change in SPPB of less than 2 points – a clinically meaningful difference.

Power for effects of Tai Chi on health care utilization can be estimated from data collected in the COLLAGE Project at Hebrew SeniorLife and Kendall Corporation. Based on 90-day retrospective self reports from 668 residents of 22 housing and low-income housing sites, the mean rate of physician visits, overnight hospitalizations, and ED visits was 2.2 total encounters per person with an over-dispersion coefficient of 1.9, combining excess variation due to both person-to-person and site-to-site variation in underlying service needs. Given these estimates, our study will have 80% power to detect a 27% reduction in total encounters over 90-days for a two-tailed test at $\alpha = 0.05$. Extrapolating conservatively to a mean annual total encounter rate of 6 encounters / person-year, the study would have 80% power to detect a reduction of just one encounter per year, assuming no increase in over-dispersion for the full-year counts. Even if over-dispersion increases 50% due to non-independence of successive 90-day intervals, the study would still have 80% power to detect a 20% reduction in mean annual total encounter rate. Previous studies of Tai Chi have reported a 30% reduction in fall rates, as well as improvements in many of the chronic illnesses (COPD, CHF, depression) that precipitate emergency, hospital, and doctor's visits. While the minimum effects of Tai Chi on measures of health care utilization and cost that are detectable with high probability will be larger if we have under-estimated year-to-year or site-to-site variation, one goal of our interim analysis is to update our estimates of these nuisance parameters and re-calculate power.

Power for the secondary cost outcome can be estimated by a two-group t-test on year-to-year change in expenditures. Total Medicare expenditure data in 2011 from the Beacon Community Medicare Project, a national sample of communities of Medicare beneficiaries that is being evaluated by our Brandeis colleagues, had a person-level standard deviation (SD) after winsorizing at the 5th and 80th percentiles of \$3,650. Year-over-year

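### Assuming 6 encounters per year is called conservative, but it flatters the claim of 80% power for an absolute reduction of one encounter; at the rate implied by the plan's source data, power is about 61%

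*Combined protocol and SAP*

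**What the plan says.** All statements are in the Combined protocol and SAP, section 8.2 (sample size determination), in the paragraph on health care utilization.

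- Source data: "Based on 90-day retrospective self reports from 668 residents of 22 housing and low-income housing sites". The average found there is reported as follows: "the mean rate of physician visits, overnight hospitalizations, and ED visits was 2.2 total encounters per person". The spread of these counts is then summarised: "with an over-dispersion coefficient of 1.9, combining excess variation due to both person-to-person and site-to-site variation".
- 90-day claim: "our study will have 80% power to detect a 27% reduction in total encounters over 90-days", at a two-sided alpha of 0.05.
- Annual claim: the rate is chosen with the words "Extrapolating conservatively to a mean annual total encounter rate of 6 encounters / person-year". The power attached to that rate is put this way: "the study would have 80% power to detect a reduction of just one encounter per year". One condition on the variance is added: "assuming no increase in over-dispersion for the full-year counts".
- Sensitivity claim: if over-dispersion is 50% higher, there is still 80% power for a 20% reduction in the annual rate.

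The paragraph does not print the annual rate that 2.2 per 90 days implies, and it gives no reason why 6 is the conservative choice. The 90-day and sensitivity effects are percentages. The one-encounter effect is absolute, and it is the only absolute effect stated for encounter counts.

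**The concern.** Section 8.1 models the counts as over-dispersed Poisson or negative binomial, so the variance grows with the mean. Whether a lower assumed rate is cautious then depends on the scale of the effect. For a percentage reduction, fewer events mean less information, and a lower rate is cautious. For a fixed reduction of one encounter, a lower rate means a smaller standard error, and the assumption favours the study. The plan attaches *conservatively* to a claim of the second kind.

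Utilization is a co-primary outcome, and the interim analysis in section 8.1 ties sample size re-estimation to a minimum effect of interest on total utilization. A reader who takes one encounter per year as the benchmark would believe that the design had 80% power for it, and might read a null Aim 2 result as stronger evidence against an effect of that size than it is.

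**Working it through.** **Inputs**

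- Source rate 2.2 per 90 days, annual rate 6 and over-dispersion φ = 1.9 (section 8.2). φ is read as variance = φ × mean.
- Sensitivity over-dispersion: 1.9 × 1.5 = 2.85.
- n = 160 per arm: 320 participants in 16 sites (section 6.2), with 1:1 allocation assumed from the coin-flip assignment of sites (section 7.1).
- Two-sided alpha 0.05. It is stated for the 90-day figure. No other alpha is given for the annual figures, so it is assumed to carry over.
- No dropout applied (assumption).

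**Formula**

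For means μ and μ − d:

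SE = √(φ × (2μ − d) / n), power = Φ(d / SE − 1.96).

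The reduction detectable with 80% power solves d = (1.96 + 0.84) × SE.

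**Step 1: reproduce the plan's three figures**

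| Claim | SE | d / SE | Power |
|---|---|---|---|
| 27% of 2.2 (d = 0.594), φ 1.9 | √(1.9 × 3.806 / 160) = 0.213 | 2.79 | 79.8% |
| 1 of 6, φ 1.9 | √(1.9 × 11 / 160) = 0.361 | 2.77 | 79.0% |
| 20% of 6 (d = 1.2), φ 2.85 | √(2.85 × 10.8 / 160) = 0.439 | 2.74 | 78.1% |

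All three fall within 2 points of the stated 80%, so this appears to be the plan's own model. A log rate ratio version differs by less than 0.4 points.

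**Step 2: annualise the source rate**

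2.2 × 365 / 90 = 8.92 per year (8.8 if multiplied by 4).

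**Step 3: change only the mean and keep the one-encounter effect**

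SE = √(1.9 × (8.92 + 7.92) / 160) = 0.447; 1 / 0.447 = 2.24; power = Φ(2.24 − 1.96) = 60.9% (61.5% at 8.8).

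| | Mean 6 | Mean 8.92 |
|---|---|---|
| Power for one encounter | 79.0% | 60.9% |
| Absolute reduction detectable with 80% power | 1.01 | 1.24 |
| n per arm for one encounter with 80% power | 165 | 252 |

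**Step 4: the same change on the percentage scale**

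| | Mean 6 | Mean 8.92 |
|---|---|---|
| Reduction detectable with 80% power, φ 1.9 | 16.9% | 13.9% |
| Power for a one-sixth reduction, φ 1.9 | 79.0% | 92.1% |
| Power for a 20% reduction, φ 2.85 | 78.1% | 91.6% |

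The direction reverses: for percentages, a mean of 6 is the cautious choice.

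**The case against.** The best defence is that *conservatively* is right on the scale that matters. With the usual log link (which section 8.1 does not state), the models named there estimate rate ratios, and the other detectable effects in the paragraph are percentages. One of six is a 16.7% reduction, and at 8.9 per year a reduction of that size has about 92% power. This stands, and it limits the point to the absolute statement. It does not rescue that statement, because the sentence gives no percentage and joins the word to a reduction of one encounter.

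It is also fair to say that the 80% figure is conditional on a stated mean and a stated over-dispersion, and that on those terms it reproduces. What fails is the description of the mean as conservative, and with it the suggestion that the power would hold at the source rate.

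Nor is 8.9 an observed annual rate. It is a linear scaling of 90-day self-reports from another sample, while the trial outcome comes from Medicare claims and also counts skilled nursing and nursing home admissions. The true rate could be nearer 6, but the plan gives no reason to expect that.

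Little can change in practice. The plan's sensitivity case, 20% of 6, is 1.2 encounters, close to 1.24. Section 8.2 warns that detectable effects may be larger if variation was under-estimated, although it does not name the mean. Recruitment has been discontinued and the trial stopped (sections 6.5, 6.7 and 8.1), so what remains is how Aim 2 results are read.

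**Conclusion.** The absolute claim is wrong as described. At the annual rate implied by the plan's source data, power for a reduction of one encounter is about 61% where the plan's assumption gives 79%, and the effect detectable with 80% power is 1.24 encounters where it gives 1.01. The stated detectable effect is therefore too small. This rests on linear annualisation, variance equal to 1.9 times the mean at both rates (the plan's own assumption of no increase), 160 per arm and two-sided alpha 0.05.

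Three stronger readings are tempting but not supported:

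- **That the utilization power statement as a whole fails.** The 27% claim does not use the annual rate, and the 20% claim is exceeded at 8.9 (about 92%).
- **That power for one encounter is really 49%.** That figure (48.5%) also changes alpha to the 0.023 set for Aim 2 in section 8.1. At that alpha, power is already 68.9% at a mean of 6. The mismatch in alpha is a separate matter.
- **That power is as low as 30%.** This lets over-dispersion grow with the mean in negative binomial fashion: 1 + (0.9 / 2.2) × 8.92 = 4.65. Applied equally at a mean of 6, the same reading gives 3.45 and only 54% power. It therefore adds a change in dispersion to the change in mean, and the plan explicitly assumes no such increase.

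**What to change.** Revise the annual sentence in section 8.2 in one of three ways:

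1. Replace the one-encounter effect with the percentage reduction and its assumed mean: about 17% at 6 encounters per year. *Conservatively* is then correct and can stay.
2. Keep an absolute effect, but state it at about 8.9 per year, labelled as scaled from the 90-day data: about 1.24 encounters with 80% power at alpha 0.05.
3. Justify 6 as the expected annual rate in this population and drop *conservatively* for the absolute claim.

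The 27% and 20% statements need no change on this account. The cost is a less favourable stated figure under option 2 and wording alone otherwise. No design or analysis step is affected.

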Data will be gathered at the housing facilities through self- and researcher-administered questionnaires, functional assessments (e.g., SPPB and Get-up-and-go tests), interactive computer programs (e.g., Trails and other cognitive tests), physiologic monitoring equipment (e.g., balance platform, gait mat, dynamometer, stadiometer), and downloaded computer files (e.g. Medicare claims). All primary study data will be recorded with computer tablets on electronic case report forms (CRF) or as digital files generated from laboratory equipment. Confidentiality will be maintained by recording subject data using a unique subject identifier. Identifiable data, such as contact information and medical record numbers, will be recorded and stored separately from the clinical study data. Any paper-based study material and any identifiable data will be kept separately in a locked file cabinet accessible by authorized study staff only. All electronic CRF data will be stored securely in an electronic data capture and management system. Raw electronic instrumentation data will be organized and saved on a private network file dedicated to the research project. All documents and electronic data will be archived for a minimum of three years, or as required by HSL IRB and federal regulations, after the completion of the clinical trial. The study will be registered at clinicaltrials.gov.

The Institute for Aging Research primarily employs the REDCap system to facilitate data management operations. REDCap is a full-featured clinical trials data management system (DMS) accessible to data entry and data analysis workstations using secure Web technologies. The REDCap product is developed and maintained by Vanderbilt University in cooperation with REDCap Consortium members including Hebrew SeniorLife. HSL hosts and maintains a dedicated instance of REDCap for use across our research enterprise.

Each research study is provided separate project workspace in which all of the study data are stored in a MySQL relational database on the private corporate network behind several firewalls and located physically within the HSL data center

9 FORESEEABLE RISKS, POTENTIAL BENEFITS, COMPENSATION AND COSTS TO PARTICIPANTS

9.1 Potential medical risks of study procedures:

There is a risk of feeling tired during the health interview, walking and balance or handgrip strength assessments. The participant will be given breaks and will be told he/she may

also ask to take a break, or may stop at any time. There is a small risk of feeling dizzy when standing up from a chair during the assessment. If this occurs the participant may sit down again. A trained research assistant will be at the participant's side at all times during the assessments. The participant will be made aware that he/she can refuse to complete a specific assessment, or if he/she becomes uncomfortable during an assessment, he/she should let the research assistant know and he/she will be allowed to skip or stop the assessment.
 
There is a risk of muscle fatigue or soreness from the Tai Chi exercises. This muscle soreness may last a few days. There is a small risk of a fall during the exercises. The Tai Chi groups will be limited to 20 persons and an experienced Tai Chi instructor will closely supervise each of the activities to minimize any risk of falling. Chairs are provided and participants will be encouraged to rest whenever needed.

9.2 Psychosocial (non-medical) risks, discomforts, inconveniences: None foreseen

9.3 Potential benefits to individual participant: Individual participants may benefit from the proposed study by learning about and possibly improving their health and function with health promotion recommendations and Tai Chi exercises. Participants may also derive a sense of satisfaction and self-esteem from contributing to an increase in overall scientific knowledge of the benefits of Tai Chi exercise

9.4 Potential benefits to study population, community, or society: The proposed research is innovative, in our opinion, because: 1) it is based on a unique conceptual model derived from complex systems theory, 2) it engages a previously understudied, underserved, and expensive population in a unique academic-community partnership, and 3) it examines important physiologic and economic outcomes that have not been previously investigated, yet can lead to a better mechanistic understanding and downstream impact of our results.


9.5 Describe provisions for medical care and available compensation in the event of injury, if any: Any participant who develops adverse events during the conduct of study protocols will be given immediate medical care at their facility and, if indicated, emergency treatment according to the housing facility's emergency plan. The participant will be referred to their primary care physician for ongoing care. The Principal Investigator will be informed immediately of any adverse events that occur during the conduct of the study protocol. There is no compensation available in the event of an injury. Cost for care in the event of an injury may be billed to the participant's insurance company. We will try to have these costs paid for, but the participant may be responsible for some of them. For example, if the care is billed to the participant's insurer, he/she will be responsible for payment of any deductibles and co-payments required by the insurer.

9.6 Remuneration for participants (e.g. goods, services, gift cards, cash, etc.): Participants will receive a check of \$10 upon completion of the first assessment,, a second check of \$10 when they have reached the 6 month timepoint of the intervention, and

another check of \$10 when they have completed the third and final assessment. We will provide snacks after Tai Chi or educational sessions. Small tokens such as pens, pins, magnets, and water bottles with the study logo will also be given out to acknowledge progress and reward participation and adherence.

Participants in the focus group will receive a stipend of \$15 per session so \$45 for participating in three focus group sessions. Participants in the withdrawal group will receive a stipend of \$15 for taking part in the individual interview. The stipend will arrive in the form of a check within 3-6 weeks following the completion of each session.

9.7 Describe any costs participants may incur during the study:

There will be no costs to participate in the study.

10 SAFETY ASSESSMENT AND STUDY MONITORING

10.1 Definitions of adverse event and serious adverse event for the study:

An adverse event (AE) is any untoward medical occurrence in a participant, whether or not is causally related to the study. An AE can therefore be any unfavorable and unintended sign (including an abnormal laboratory finding, for example), symptom or disease temporally associated with the study. Adverse events will be recorded on the appropriate case report forms and source documents. The investigator and/or trained staff member will evaluate all adverse events as to their severity and relation to the test article. The severity of adverse events will be graded as follows:

Mild: Awareness of a sign or symptom but easily tolerated and are of minor irritant type causing no loss of time from normal activities. Symptoms do not require therapy or a medical evaluation; signs and symptoms are transient.

Moderate: Events introduce a low level of inconvenience or concern to the participant and may interfere with daily activities, but are usually improved by simple therapeutic measures; moderate experiences may cause some interference with functioning.

Severe: Events interrupt the participant's normal daily activities and generally require systemic drug therapy or other treatment, they usually are incapacitating.

Life Threatening: The participant was at immediate risk of death from the AE as it occurred.

Expectedness: ADs must be assessed as to whether they were expected to occur or unexpected, meaning not anticipated based on current knowledge found in the protocol. Categories are:

- Unexpected - nature or severity of the event is not consistent with information about the condition under study or intervention in the protocol or consent form.
- Expected - event is known to be associated with the intervention or the condition under study.

The Investigator will also assess the relationship of any adverse event to study, based upon available information, using the following guidelines:

- Definitely Related: The adverse event is clearly related to the investigational procedure - i.e. an event that follows a reasonable temporal sequence from

administration of the study intervention, follows a known or expected response pattern to the suspected intervention, that is confirmed by improvement or stopping and reappearance of the event on repeated exposure and that could not be reasonably explained by the known characteristics of the subject's clinical state.

- **Possibly Related:** An adverse event that follows a reasonable temporal sequence from administration of the study intervention follows a known or expected response pattern to the suspected intervention, but that could readily have been produced by a number of other factors.
- **Not Related:** The adverse event is clearly not related to the investigational agent/procedure - i.e. another cause of the event is most plausible; and/or a clinically plausible temporal sequence is inconsistent with the onset of the event and the study intervention and/or a causal relationship is considered biologically plausible.

A serious adverse event is any experience that results in any of the following outcomes:

- death,
- is life threatening,
- inpatient hospitalization or prolongation of hospitalization,
- a persistent or significant disability/incapacity.

Important medical events that may not result in death, be life-threatening, or require hospitalization may be considered a serious adverse event when, based upon appropriate medical judgment, they may jeopardize the patient or participant and may require medical or surgical intervention to prevent one of the outcomes listed in this definition.

10.2 Adverse event (AE) reporting (method, distribution and time frame):

Adverse events will be reported to the Hebrew SeniorLife Institutional Review Board (IRB) and the NIA according to established guidelines. All serious adverse events (SAEs) will be reported promptly to the Safety Monitoring Board and the IRB, in accordance with IRB requirements.

When SAE's occur that are unanticipated they will be reported to the NIA Program Administrator and to the DSMB Chair or designated DSMB member within 48 hours of the study's knowledge of the SAE. A death would be reported expeditiously, within 24 hours of the study's knowledge. A summary of all other SAE's will be reported to the NIA Program administrator and the DSMB quarterly, unless otherwise requested by the DSMB.

Any participant who develops adverse events during the conduct of study protocols will be given immediate medical care at their facility and, if indicated, emergency treatment according to the housing facility's emergency plan. The participant will be referred to their primary care physician for ongoing care. The Principal Investigator will be informed immediately of any adverse events that occur during the conduct of the study protocol.

10.3 Process for data and safety monitoring:

Safety monitoring procedures will be implemented and reviewed by a Data Safety Monitoring Board (DSMB), in accordance with NIA safety policies for human intervention studies. The criteria for discontinuing a participant's participation include the participant's request, as well as any life-threatening or potentially disabling event, including syncope, an injurious non-accidental fall, hemodynamic collapse, stroke, transient ischemic attack, dysrhythmia, renal insufficiency, angina, myocardial infarction, anaphylaxis, acute hemorrhage, or hospitalization for acute illness. These adverse events will be recorded and included in the database. If the participant recovers from a potentially serious event, he/she may re-enter the study if they are assessed safe to return. In this situation, we will ask the participant's primary MD to assess the participant's medical fitness to return to the study. To do this, we will send the attached letter to the participant's MD, with the participant's permission and request that the participant's MD sign off that it is medically safe for the participant to resume their participation in the study. If a determination about continued participation cannot be made according to these criteria, the adverse event report will be faxed to the chair of the Data Safety Monitoring Board who will make a decision with members of the Board.

A DSMB will be established for this project. This will consist of nationally recognized experts in geriatric medicine, biostatistics, senior housing, and clinical research. The chairperson will be an individual who is readily accessible for consultation in the local area. At the first meeting of the DSMB, members will review the study protocol and safety-monitoring plan.

Prior to the start of the study the DSMB will review the IRB approved protocol and procedure manual, with regard to participant safety, recruitment, randomization, intervention, data management, quality control, and the informed consent document. The Board will recommend any necessary changes of the protocol to the PIs and will review and approve revisions. The Board will identify relevant data parameters and the format of the information to be regularly reported.

The Board will then meet biannually to review standardized reports. They will review the progress of recruitment and retention of participants, compliance with the protocol, and operating procedures. If they raise concerns about safety issues, they may request additional data and propose specific analyses. They will make recommendations to the PI regarding recruitment, retention, compliance, and safety issues, and will send a written report to the Program Administrator following each meeting. The DSMB will be sent reports of research activity and summaries of safety monitoring information before each meeting.

10.4 If this is a multi-site study, indicate how modifications of study procedures or materials will be communicated across sites, as well as communication of adverse events, or other issues affecting the research:

This is not a multi-site study.

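### One of the three grounds for coding an adverse event as *Not Related* (section 10.1) is inverted: it names a biologically plausible causal link

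*Combined protocol and SAP*

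**What the plan says.** Section 10.1 sets a three-level causality scale: *Definitely Related*, *Possibly Related* and *Not Related*. It is operative text: "The Investigator will also assess the relationship of any adverse event to study, based upon available information, using the following guidelines". The same section allows the evaluation of severity and relation to be made by the investigator, a trained staff member, or both.

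The *Not Related* category opens with "The adverse event is clearly not related to the investigational agent/procedure". It then explains that condition through three grounds:

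1. "another cause of the event is most plausible";
2. "a clinically plausible temporal sequence is inconsistent with the onset of the event and the study intervention";
3. "and/or a causal relationship is considered biologically plausible".

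The category directly above it, *Possibly Related*, covers an event with reasonable timing that "follows a known or expected response pattern to the suspected intervention, but that could readily have been produced by a number of other factors".

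The clause stands in the current text, and the sentence is complete, with no sign of redaction. Nothing elsewhere in the document corrects or qualifies it.

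**The concern.** A biologically plausible mechanism is a reason to suspect the intervention. Here it is listed as a reason to clear it. Because the grounds are alternatives, the third is enough on its own when the list is read literally.

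What is at stake is the causality label on individual events. The scale has no intermediate step such as *unlikely*, so a misapplied clause moves an event from possible attribution straight to none. The trial's own named exercise risks are the natural candidates: section 9.1 lists muscle fatigue or soreness and a small risk of falling as risks of the Tai Chi sessions. Relatedness codes could then be too favourable in the safety summaries sent to the DSMB (section 10.3) or in the planned publications (section 13.1). Written definitions matter most where a staff member other than the investigator does the coding, which section 10.1 permits.

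**Working it through.** There is no figure to recompute. The check sets the parts of the definition side by side and then tests them on an example.

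**Direction of each part of *Not Related***

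| Part | Content, paraphrased | Direction |
|---|---|---|
| Lead-in | Event is clearly unrelated | Against causation |
| Ground 1 | A different cause is the most plausible one | Against causation |
| Ground 2 | Timing does not fit the intervention | Against causation |
| Ground 3 | A causal link is biologically plausible | For causation |

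Ground 3 is the only part that points the other way.

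**Test on a hypothetical event.** Take muscle soreness that starts soon after a Tai Chi class, where other factors could also have produced it but none stands out as the most plausible cause.

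- *Possibly Related*: the timing is reasonable, section 9.1 makes soreness an expected response, and other factors could explain it. The definition is met.
- *Not Related*, ground 1: not met, because no other cause is the most plausible.
- *Not Related*, ground 2: not met, because the timing fits.
- *Not Related*, ground 3 as written: met, because a mechanism is plausible.

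The list of grounds therefore admits the event to *Not Related* while it also meets *Possibly Related*. Section 10.1 gives no rule for choosing between two categories that both apply.

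**Same event with plausible changed to implausible.** Ground 3 is no longer met, and only *Possibly Related* remains. All three grounds then point the same way as the lead-in.

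**Where the causality code is used**

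| Procedure | Section | What it depends on |
|---|---|---|
| Prompt SAE reporting to the safety board and IRB | 10.2 | Seriousness |
| 48-hour report | 10.2 | Serious and unanticipated: "When SAE's occur that are unanticipated they will be reported to the NIA Program Administrator" |
| 24-hour report | 10.2 | Death |
| Quarterly summary | 10.2 | All other SAEs |
| Discontinuing a participant | 6.7, 10.3 | Type of event (10.3 adds the participant's request) |
| Fall analysis | 7.1, 8.1 | Counts of falls; falls are asked about in monthly calls |
| Interim efficacy and futility rule | 8.1 | The co-primary outcomes |

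None of these names relatedness. Expectedness, in section 10.1, is a separate assessment and does not use the clause. One route cannot be checked: section 10.2 refers the reporting of adverse events in general to established guidelines that the document does not reproduce.

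**The case against.** The strongest reply is that the lead-in governs. The three grounds are offered as an explanation of being clearly unrelated, so an event with a plausible link to Tai Chi fails the condition before the grounds are reached, and *Possibly Related* sits immediately above to receive it. Two of the three grounds point the right way, and the contradiction is visible enough that a careful assessor would recognise a lost negative. Recruitment has been discontinued (section 6.5) and the remaining interventions are being stopped (section 6.7), so little prospective coding is left.

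Most of this stands, and it limits the consequence. It does not make the sentence right. The clause contradicts its lead-in, and an assessor has to notice that and set the clause aside, which the text does not instruct. The stopping of the trial does not close the matter either. Wave 1 had 12-month data at the interim analysis and two wave 2 pairs had interventions under way, so coded events may already exist, and the results are to be published.

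A reader might infer more from the clause than the documents support:

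- *That the whole causality scale is reversed.* Only one ground in one category is.
- *That plausibly related events were in fact coded as unrelated.* No coded event is shown. Could be miscoded is the most the text allows.
- *That SAE reports to the DSMB, IRB or NIA were missed or delayed.* The triggers stated in section 10.2 do not turn on relatedness.
- *That the fall results or the futility decision are affected.* Neither uses the causality code.

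**Conclusion.** The clause is wrong as written and should be corrected. It is an internal inconsistency in a safety definition, not a choice of analysis method, and its severity is minor.

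Its size is one of three alternative grounds within one of three categories. The number of events exposed cannot be given, because the documents report no adverse event counts by causality code. It could be zero, if every assessor followed the evident intent. At most it is the set of events coded *Not Related* that had a plausible link to the intervention. The exposure is to the causality label alone.

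The conclusion rests on two assumptions: that the case report form and procedure manual, which are not part of the document, either repeat this wording or leave assessors to rely on it; and that the unreproduced guidelines in section 10.2 do not add a relatedness filter for non-serious events. If the working forms carry the correct wording, only the protocol text needs repair. If the guidelines do filter on relatedness, the reach extends to the reporting of some non-serious events.

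**What to change.** 1. In the third ground for *Not Related* in section 10.1, change biologically plausible to biologically implausible.
2. Confirm which wording the case report form and the procedure manual carry, and align them with the corrected text.
3. Re-check events already coded *Not Related* against the corrected definition, starting with falls and musculoskeletal events in the Tai Chi arm. Record any code that changes and pass it to the DSMB and into the published safety table.

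The cost is one word, a look at two working documents and a short review of coded events. No analysis in section 8 needs to change.
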